idebenone therapy and CRR, where possible compared to untreated control patients.

The treatment duration in RHODOS was 6 months and a larger proportion of idebenone-treated patients presented with CRR in VA compared to placebo. However, data from Santhera's ongoing Expanded Access Program (EAP) indicates that prolonged treatment can increase both the proportions of patients with CRR of VA and the magnitude of the recovery observed. Furthermore, data from the RHODOS and from the EAP provide evidence that the LHON-causative mutation harboured is prognostic of CRR in VA. Therefore, secondary objectives of this study are to provide information on the effect of treatment duration on both the proportions of patients presenting with CRR and on the magnitude of any response with increasing treatment time and on the influence of the mutation harboured on CRR rate compared to spontaneous CRR (sCRR) in untreated control patients.

The study will also allow the assessment of the safety and tolerability of long-term treatment with idebenone, with particular emphasis on the proportion of patients experiencing elevated Liver Function Tests (LFTs) or changes in blood cell counts.

Number of Centres

Approximately 35

Multinational study with US sites operating under IND and EU sites not operating under IND.

Number of Patients

80 patients presenting ≤1 year after the onset of symptoms will be enrolled to ensure 61 provide VA assessments following 12 months of idebenone treatment (primary endpoint).

80 patients presenting >1 year after the onset of symptoms will be enrolled to ensure 61 provide VA assessments following 12 months of idebenone treatment (secondary endpoint). Patients will be stratified according to time since onset of symptoms with a maximum of 30 patients to be enrolled in any of the strata of >1 - \leq 2 years, >2 - \leq 3 years, >3 - \leq 4 years and >4 - \leq 5 years since onset of symptoms.

Inclusion Criteria

- 1. Impaired visual acuity in affected eyes due to LHON
- 2. No explanation for visual loss besides LHON
- 3. Age \geq 12 years
- 4. Onset of symptoms ≤5 years prior to Baseline
- 5. Confirmation of either G11778A, G3460A or T14484C LHON mtDNA (for the ITT population, not required for enrolment)
- 6. Written informed consent obtained from the patient
- 7. Ability and willingness to comply with study procedures and visits

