1.2 Rationale for the Study

The randomized, placebo-controlled RHODOS (SNT-II-003) trial (Klopstock et al., 2011), the retrospective cohort study of Carelli et al., (2011), Santhera's ongoing Expanded Access Program (EAP) and several case reports (summarized in Gueven and Faldu, 2013), provide evidence that idebenone promotes the recovery of VA in patients with LHON. However, due to the nature of these datasets, this evidence is not considered comprehensive.

In view of the urgent medical need and poor prognosis of LHON if untreated, a randomized, placebo-controlled study to provide comprehensive data is not considered feasible in LHON. An open-label study is therefore considered the most appropriate strategy for gathering additional evidence for the efficacy of idebenone in the treatment of LHON. The primary objective of this study is therefore to compare the outcomes for patients treated with idebenone ≤1 year of the onset of symptoms in this study with those of matching untreated patients from an external natural history control group generated in a historical case record survey (CRS).

In RHODOS, LHON patients enrolling up to 5 years after the onset of symptoms of disease were treated with idebenone. Whilst natural history VA outcomes data collected from LHON patients early in the course of the disease is available, relatively little reliable natural history VA outcomes data is available from patients with longer disease durations. The primary endpoint of this study will therefore compare the VA outcomes for patients treated with idebenone ≤1 year of the onset of symptoms with matching natural history control data. Secondary endpoints will include outcomes for patients treated with idebenone >1 year after the onset of symptoms. Since LHON

is known to lead to the apoptotic loss of retinal ganglion cells where the extent of loss increases with time since onset of disease, this study will explore further the relationship between time since onset at the initiation of idebenone therapy and CRR, where possible compared to untreated control patients.

The treatment duration in RHODOS was 6 months and a larger proportion of idebenone-treated patients presented with CRR in VA compared to placebo. However, data from Santhera's ongoing Expanded Access Program (EAP) indicates that prolonged treatment can increase both the proportions of patients with CRR of VA and the magnitude of the recovery observed.

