- The selected baseline value and the follow-up VA assessment within12±3 months in the same eye will be included in the external natural history control group for the eyes in the OLS with baseline >1 year after the onset of symptoms
- It should be noted that different cuts (various baseline with corresponding follow-up VA values) from the same eye can be used multiple times, both for the analysis of the primary endpoint (only once) and for the analysis of eyes with baseline >1 year after the onset of symptoms (not more than once within each of the four bins defined above)

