8.5.2 Matching algorithm for the secondary endpoints

The external NH control set for the eyes with BL >1 year since onset of symptoms in the LEROS ITT population will be generated as follows (section 19.1 presents the matching algorithms using workflow diagrams):

SNT-IV-005 Statistical Analysis Plan

Confidential

- 1. All available eyes in the external NH control set will be considered, regardless of whether the eye in question was used in the control group for the primary objective or not.
- 2. All VA assessments >1 year after the onset of symptoms are considered as potential BL values.
- 3. If a potential BL value does not have a follow-up VA assessment within 12±3 months, it will be excluded.
- 4. The remaining potential BL values will be categorized in the following time since onset bins: >1-2 years, >2-3 years, >3-4 years or >4-5 years.
- 5. If there are several potential BL values for the same eye in the same bin, the eye with the BL value closest to the midpoint of the bin will be selected.
- 6. The selected BL value and the follow-up VA assessment within 12±3 months in the same eye will be included in the external NH control set for the eyes in the LEROS ITT population with BL >1 year after the onset of symptoms.

The described process will be applied for the 6, 18 and 24 month time points for the eyes with BL >1 year after the onset of symptoms.

It should be noted that different cuts (various BL with corresponding follow-up VA values) from the same eye can be used multiple times, both for the analysis of the primary endpoint (only once) and for the analysis of eyes with BL>1 year after the onset of symptoms (not more than once within each of the four bins of follow-up months defined in Table 1).

9 General statistical considerations

Continuous data will be summarized using the number of observations (n), mean, standard deviation (SD), standard error of the mean (SEM), median, 1st and 3rd quartile, minimum and maximum.

Categorical data will be presented in contingency tables with frequencies and percentages.

The listings will be generally sorted by center and patient number (and by visit, if applicable).

Graphical representations will be used as appropriate.

In general, apart from the safety population, data will be summarized by onset of symptoms

- ≤ 1 year after the onset of symptoms;
- >1 year after the onset of symptoms

, as defined in section 16.

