12.1 Primary endpoint

Endpoint: Proportion of eyes with clinically relevant recovery (CRR) of visual acuity from Baseline (BL) or in which BL VA better than 1.0 logMAR was maintained at Month 12 in patients treated with Raxone® ≤1 year after the onset of symptoms, compared to matching external natural history control group. CRR definition is presented in section 16.

Analysis sets: Primary endpoint analysis will use all LEROS mITT eyes that are ≤1 year since onset of symptoms at BL and have the Month 12 assessment. External NH control set is generated as described in section 8.5.1 (Matching algorithm for the primary endpoint), using VA assessments within 12±3 months from BL.

Analysis method: The primary endpoint will be analysed using a logistic regression model. The binary response will be used as the dependent variable. The independent variables include the treatment group (Raxone® treated patients versus untreated control group), gender (male, female) and mutation group (G11778A, G3460A, T14484C) as fixed factors.

The difference between the Raxone® treated patients versus NH group will be estimated with odds ratio, two-sided 95% confidence intervals and two-sided p-values

```
proc logistic;
  class treatment gender mutation / param=ref;
  model CRB(event='1') = treatment mutation gender / link=logit clodds=pl;
  oddsratio treatment;
run;
```

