  class treatment gender mutation / param=ref;
  model CRB(event='1') = treatment gender mutation / link=logit clodds=pl;
  ods output ParameterEstimates = ParameterEstimates;
  ods output CLOddsPL = CLOddsPL;
run;
     STEP 5: calculate the logistic analysis combined results*/
proc mianalyze parms(classvar=classval)= ParameterEstimates.;
   modeleffects treatment gender mutation;
run;
```

```
STEP 6: calculate the combined results odds ratio */
/* Transform estimates */
data calculated odds ratio 1;
   label or_value = 'Log odds ratio value'
        or stderr = 'Log odds ratio SE';
  set CLOddsPL;
     or value = log(OddsRatioEst);
     or_stderr= (log(uppercl)-log(lowercl))/(2*1.96);
run;
    Combine transformed estimates */
proc sort data= calculated_odds_ratio_1; by Effect; run;
proc mianalyze data= calculated_odds_ratio_1;
       by Effect;
       modeleffects or_value;
       stderr or_stderr;
       ods output ParameterEstimates = calculated odds_ratio_2;
     run;
     Back-transform combined values */
data calculated odds ratio 3;
   label estimate back = 'Odds ratio'
        lcl back = 'LCL Odds ratio'
        ucl_back = 'UCL Odds ratio';
       set calculated_odds_ratio_2;
       estimate back = exp(estimate); *pooled odds ratio;
       lcl_back=estimate_back*exp(-1.96*stderr); *pooled lower limit;
       ucl_back=estimate_back*exp(+1.96*stderr); *pooled upper limit;
     run;
```

Through inverse probability of treatment

Propensity score will be calculated by means of logistic regression with treatment as dependent variable. Independent variables include gender (male, female), mutation group (G11778A, G3460A, T14484C), age, time since symptoms onset in months and VA at BL (logMAR) as factors.

The same primary model as described above will be applied with the inverse probability weight.

```
SAS code to calculate the propensity score (values: Raxone® treated patients = 1; NH = 0)
proc logistic data=CRB dataset;
  class gender mutation / param=ref;
  model treatment(event='1') = gender mutation age time onset bl va;
  output out=psdataset pred=ps;
run;
data analysis dataset;
  set psdataset;
  if treatment = 1 then ps weight = 1/ps;
  else if treatment = 0 then ps weight = 1/(1 - ps);
run;
SAS code to proceed with the endpoint regression analysis
proc logistic data= analysis dataset;
  class treatment gender mutation / param=ref;
   model CRB(event='1') = treatment gender mutation / link=logit clodds=pl;
  oddsratio treatment;

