12.2 Efficacy Secondary Endpoints

Endpoint: Components of the primary endpoint: proportion of eyes with CRR of VA from BL at Month 12 compared to matching external NH control group

Analysis method: This endpoint will be analysed with methods similar as for analysing the primary endpoint as defined in section The criteria of inclusion/exclusion for the pre-planned indirect comparison of the primary endpoint against an external natural history control group, where it is only considered who are carriers of only one of the three major LHON mtDNA (G11778A, G3460A or T14484C). Due this criterion, efficacy analysis where there is an indirect comparison to the external natural history control group, will be based on the mITT population.

Primary endpoint 12.1.

Endpoint: Components of the primary endpoint: proportion of eyes in which BL VA better than 1.0 logMAR was maintained at Month 12 compared to matching external NH control group

Analysis method: This endpoint will be analysed with methods similar as for analysing the primary endpoint as defined in section The criteria of inclusion/exclusion for the pre-planned indirect comparison of the primary endpoint against an external natural history control group, where it is only considered who are carriers of only one of the three major LHON mtDNA (G11778A, G3460A or T14484C). Due this criterion, efficacy analysis where there is an indirect comparison to the external natural history control group, will be based on the mITT population.

Primary endpoint 12.1.

Endpoint: Proportion of eyes in patients treated with Raxone[®]>1 year after the onset of symptoms with CRR of VA from BL or in which BL VA better than 1.0 logMAR was maintained at Month 12 compared to external NH control group

Analysis method: This endpoint will be analysed with methods similar as for analysing the primary endpoint as defined in section The criteria of inclusion/exclusion for the pre-planned indirect comparison of the primary endpoint against an external natural history control group, where it is only considered who are carriers of only one of the three major LHON mtDNA (G11778A, G3460A or T14484C).

Study: SNT-IV-005

Due this criterion, efficacy analysis where there is an indirect comparison to the external natural history control group, will be based on the mITT population.

Primary endpoint 12.1.

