13.8 Other safety variables

No other safety data are to be analysed.

V1.0 07 June 2021

14 Deviations from the analyses planned in the current study protocol

There are currently no deviations from the CRS-1 CSP (version 1), CRS-2 CSP (version 1.0) and SNT-IV-005 CSP version 3.0 dated 06 March 2019 and SNT-IV-005 CSP addendum COVID-19 version1.0 dated 29 May 2020

15 Data analysis procedures

Statistical data analysis will be performed by 4Pharma Ltd according to current SAP.

Statistical analysis, tables and patient data listings will be performed with SAS® version 9.4 or higher for Windows (SAS Institute Inc., Cary, NC, USA).

16 Definitions

2nd eye onset

Most recent affected eye at Baseline.

Baseline (BL)

LEROS BL

NH BL

Best Visual Acuity

VA of the eye with best logMAR at the visit. However, if both eyes are off-chart, regardless of the VA, both eyes are considered as best eye.

Note: best eye at BL may not be the same as best eye at 6, 18 and 24 months or last assessment.

Clinical Relevant Benefit (CRB)

Defined as the composite of CRR and CRS, i.e, if the eye/patient has a CRR and/or a CRS then the eye/patient has also a CRB.

Clinical Relevant Recovery (CRR)

CRR is defined as improvement

or

- from "off-chart" (the equivalent of CF, HM, LP or NLP) VA to at least 1.6 logMAR value
 - of at least 0.2 logMAR value within "on-chart". Clinical Relevant Stabilization (CRS)

Is defined as maintenance of VA <1.0 logMAR in eyes with VA <1.0 logMAR at BL.

Clinical Relevant Worsening (CRW)

For any "on-chart" VA, CRW is defined as the disability to read at least 10 additional letters (equivalent to two chart lines) or a worsening to off-chart values (the equivalent of CF, HM, LP or NLP).

SNT-IV-005 Statistical Analysis Plan

Confidential

Delta onset

Is the time between symptoms onset of both eyes: date 2nd symptoms onset – date 1st symptoms onset. Patients will not be considered for calculating Delta onset if only one eye is affected or both eyes have the same date of symptom onset.

Months in Treatment

Months in treatment is only applied to LEROS patients. It is defined as time since BL to last follow-up during treatment period.

Nadir

Is the defined when VA reaches its worst point (highest logMAR or off-chart value). Time of nadir is the first time that nadir is reached.

Off-Chart

It is considered off-chart any VA entered as

- CF, HM, LP or NLP
- Any value above 1.68 logMAR

Patients ≤1 year after the onset of symptoms

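### In the >1-year comparison, repeated control rows from the same eye are analysed as independent and onset bin is left out of the model, so the CI is probably too narrow and the result open to bin-mix confounding

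*SAP*

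**What the plan says.** SAP 8.5.2 takes every natural-history VA later than 1 year after onset that has a follow-up at 12±3 months as a possible baseline. It sorts these into onset bins (>1-2, >2-3, >3-4 and >4-5 years), removes duplicates of an eye within a bin only, and pools everything selected into one control set. The reuse is deliberate: "It should be noted that different cuts (various BL with corresponding follow-up VA values) from the same eye can be used multiple times". Protocol 9.2.2 sets the same limit per eye, "not more than once within each of the four bins defined above", where the bins are the onset bins. The primary (≤1 year) comparison uses each control eye once.

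For the >1-year Month 12 endpoint, SAP 12.2 states: "This endpoint will be analysed with methods similar as for analysing the primary endpoint as defined in section", and points to 12.1. The model there is "model CRB(event='1') = treatment mutation gender / link=logit clodds=pl", run in PROC LOGISTIC. It has no repeated, random or cluster-robust component and no term for time since onset.

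Time since onset enters one model only, the propensity score in SAP 12.1.1, whose covariates include "age, time since symptoms onset in months and VA at BL (logMAR) as factors". That analysis is listed as a sensitivity analysis of the primary endpoint. On the LEROS side, the Protocol synopsis controls the onset mix: "Patients will be stratified according to time since onset of symptoms with a maximum of 30 patients" in any yearly stratum. No such control exists for the natural-history rows.

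**The concern.** This is the analysis for the first secondary objective, and SAP section 9 applies two-sided testing at 0.05 to it. Two separate problems arise.

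**Precision.** If rows from one eye are positively correlated, counting them as independent overstates the control information. Positive correlation is likely for this composite. SAP section 16 defines stabilisation as "maintenance of VA <1.0 logMAR in eyes with VA <1.0 logMAR at BL", a persistent state: an eye that stays better than 1.0 logMAR is a responder in every bin it enters. The argument does not carry over to CRR alone, because one cut's follow-up can be the next cut's baseline, which pushes the correlation towards zero or below.

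**Confounding.** The bins select control rows; they do not match, weight or stratify the two groups. If untreated response varies with time since onset, a different bin mix produces a difference with no drug effect. The protocol itself expects the control mix to be uneven: "relatively little reliable natural history VA outcomes data is available from patients with longer disease durations". SAP Table 11-2 tabulates time since onset for the matched sets, so an imbalance would be seen but not adjusted for.

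**Working it through.** **The plan's own figure.** The >1-year group copies the size of the primary comparison: 110 LEROS eyes at 40% against 175 control eyes at 22%, two-sided 0.05, 90% power (SAP section 6).
- Pooled rate = (44 + 38.5)/285 = 0.2895.
- Null SE = sqrt(0.2895 × 0.7105 × (1/110 + 1/175)) = 0.0552. Alternative SE = sqrt(0.24/110 + 0.1716/175) = 0.0562.
- Power = Φ((0.18 − 1.96 × 0.0552)/0.0562) = 0.899.

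So 110 reproduces, on the footing that every eye is independent.

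**Ceiling on rows.** One row per bin × 4 bins = 4 per control eye; × 2 eyes = 8 per control patient.

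**Effect of reuse on that illustration.** Take the 175 as control rows, with m rows per eye and within-eye correlation ρ (both assumed). The control design effect is D = 1 + (m − 1)ρ. The SE multiplier is k = sqrt((1/110 + D/175)/(1/110 + 1/175)), and the true alpha is 2(1 − Φ(1.96/k)).

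| m | ρ | D | k | alpha |
|---|---|---|---|---|
| 2 | 0.2 | 1.2 | 1.04 | 0.059 |
| 2 | 0.6 | 1.6 | 1.11 | 0.077 |
| 4 | 0.2 | 1.6 | 1.11 | 0.077 |
| 4 | 0.6 | 2.8 | 1.30 | 0.132 |

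The odds ratio of 2.36 has a naive 95% CI of 1.40-3.99; at m = 4, ρ = 0.6 it becomes 1.16-4.81. With ρ = −0.1, alpha would be 0.046 (m = 2) to 0.037 (m = 4).

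**Simulation by patient.** Assumed: 60 control and 55 LEROS patients, two eyes each, 20% response, no treatment effect, Wald test of the log odds ratio, 10,000 replicates. Here extra cuts add rows, so the effect is milder than in the table above. Type I error at 1/2/3/4 cuts per control eye:

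| ICC | Same-eye dependence only | Same-eye plus fellow-eye |
|---|---|---|
| 0.1 | 0.048/0.050/0.052/0.057 | not run |
| 0.3 | 0.051/0.062/0.064/0.066 | 0.088/0.096/0.116/0.120 |
| 0.5 | 0.047/0.066/0.078/0.079 | 0.114/0.153/0.161/0.169 |
| 0.65 | 0.049/0.071/0.085/0.091 | 0.120/0.167/0.193/0.202 |

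Closed-form check at ICC 0.65 and 4 cuts (480 control rows, 110 LEROS eyes): D = 2.95, k = sqrt((1/110 + 2.95/480)/(1/110 + 1/480)) = 1.168, alpha 0.093, against 0.091 simulated.

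With sparser reuse (60/30/10% of control patients having 1/2/3 cuts per eye), at ICC 0.3/0.5/0.65, reuse alone gives 0.057/0.069/0.074, and 0.102/0.137/0.166 with fellow eyes. Patient-clustered variance gives 0.044-0.052 throughout.

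**Sign of the correlation.** A toy model of five yearly VAs (stable eye mean 1.2-1.6 logMAR, between-eye SD 0.4-0.6, visit noise SD 0.1-0.3; all assumed) gave an average same-eye correlation of +0.06 to +0.75 for the composite and −0.12 to −0.01 for CRR alone.

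**Bin mix.** Spurious difference = Σ(LEROS share − control share) × rate in bin, with assumed untreated rates of 25/18/12/8%. The cap of 30 in 80 allows at most 37.5% of LEROS in one bin. LEROS at 30/30/10/10 has an expected rate of 18.625%; at 20/20/20/20, 15.75%.

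| Control mix (%) | Control rate (%) | LEROS 30/30/10/10 | LEROS 20/20/20/20 |
|---|---|---|---|
| 10/20/30/40 | 12.9 | +5.7 | +2.9 |
| 25/25/25/25 | 15.75 | +2.9 | 0.0 |
| 40/30/20/10 | 18.6 | 0.0 | −2.9 |
| 60/25/10/5 | 21.1 | −2.5 | −5.4 |

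As odds ratios, the extremes are (0.18625/0.81375)/(0.129/0.871) = 1.55 and (0.1575/0.8425)/(0.211/0.789) = 0.70, with no drug effect.

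**The case against.** The strongest point is textual. The closing sentence of SAP 8.5.2 limits reuse by bins of follow-up months in a Table 1. The nearest table, 8-1, has follow-up columns 6, 12, 18 and 24. Read literally, an eye would enter the Month 12 set once, and the SAP overrides the protocol. But steps 4-6 of the same section generate one row per onset bin, the same sentence allows multiple use, and Protocol 9.2.2 names the onset bins. The sentence is a defect to correct, not a safeguard.

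Second, most of the larger error figures come from fellow-eye correlation, which the primary analysis shares. This stands: reuse alone accounts for 6-9%, and for 6-7% under sparse reuse. Sparse reuse is the more plausible case, since the second survey (SNT-CRS-002) required only two VA assessments within 5 years. At ICC 0.1 the effect of reuse is negligible.

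Third, the bin rates are assumed, and equal rates give no bias. If controls cluster early, as the protocol suggests, these figures run from 0.0 to −5.4 points, against idebenone. That also stands, and gives the sponsor its own reason to adjust.

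Fourth, Protocol 9.4.2 plans a GLIMMIX analysis. It addresses incomplete data, states no link between cuts or fellow eyes, and is not carried into SAP 12.1.1.

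**Conclusion.** The concern holds. The plan as written pools repeated cuts of one eye and analyses them with a model that has neither clustering nor onset bin. For the >1-year composite, the interval is too narrow if rows of the same patient are positively correlated, which is likely. Under the assumed inputs, error is about 6-9% from reuse alone for ICC 0.3-0.65 with 2-4 cuts per eye, close to 5% at ICC 0.1, and 10-20% with fellow-eye correlation, of which 9-12% exists at one cut. The bin-mix shift of −5.4 to +5.7 points rests on assumed rates and mixes, and its direction cannot be known from the documents. Rows per eye, correlation and bin counts are not stated in the plan, so these are ranges, not estimates. The claim of a too-narrow interval does not extend to CRR alone, and the primary test has no repeated cuts. This should be corrected, because it affects the interval and p-value for a named secondary objective.

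**What to change.** In SAP 12.2, for the >1-year endpoint:
- use GEE or a robust variance clustered on patient, covering both eyes and all cuts;
- add the four-level onset bin as a fixed factor, with a pre-stated rule for collapsing sparse late bins;
- report control rows, eyes and patients per bin.

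In the last sentence of SAP 8.5.2, replace the reference to follow-up-month bins in Table 1 with the onset bins of step 4.

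The cost is SAP wording and code; the bin variable already exists. The model gains three parameters and the interval will be wider. Clustering and onset bin do not remove confounding by other factors such as baseline VA.
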